- Patients aged 18-80 years who have developed a pseudomeningocele following elective intracranial surgery.
- Diagnosed fluctuation during clinical examination after the surgery, Pseudomeningocele Palpation Scale (PPS), II-IV

I No or minimal fluctuation; underlying bone is clearly palpable with light palpation.

II Definite fluctuation; underlying bone or muscle is palpable with moderate pressure.

III Marked fluctuation; underlying structures are palpable only with firm pressure.

IV Tense lesion; painful and/or erythematous; underlying structures are not palpable even with firm pressure.

Light palpation: minimal pressure without causing discomfort

Moderate pressure: increased pressure causing awareness but no pain

Firm pressure: strong pressure causing discomfort or mild pain

- Willing and able to give informed consent.
- No prior history of previous cranial or spinal surgical intervention.

Exclusion Criteria:

- Patients with pseudomeningocele due to emergency or trauma-related surgeries.
- Known or suspected infection at the pseudomeningocele site at the time of recruitment.
- Severe comorbid conditions preventing participation (e.g., terminal illness, severe organ failure).
- Patients with conditions that require urgent surgical intervention not related to pseudomeningocele management.

5. Interventions

Interventional Arm:

- Patients will undergo one of the following procedures based on clinical judgment:
 1. **Revision surgery:** Surgical intervention to drain the pseudomeningocele and ensure proper wound closure.
 2. **Lumbar drainage insertion:** Placement of a lumbar drain to facilitate cerebrospinal fluid (CSF) diversion.
 3. **Simple puncture:** Needle aspiration of the pseudomeningocele under sterile conditions.

Conservative Arm:

- Patients will receive conservative management, with no surgical procedures other than the application of skin sutures if required. Monitoring and wound care will be provided.
-

6. Outcomes

Primary Outcome:

- **New onset of wound CSF leakage or tension pseudomeningocele necessitating revision surgery**

Secondary Outcomes:

- **Infection rate:**
Incidence of infection related to the pseudomeningocele or any interventions, including signs of local infection, meningitis, or systemic sepsis, within 1 year.
 - **Functional recovery (GOSE):**

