The Glasgow Outcome Scale–Extended (GOSE) will be assessed at 1 year post-surgery to evaluate functional outcomes and quality of life. GOSE scores range from 1 (death) to 8 (upper good recovery).
 - **Pseudomeningocele absorption on CT or MRI:**
The primary outcome is the resolution or reduction of the pseudomeningocele, assessed through CT or MRI at **4 months** and **1 year** post-surgery. Scans will be reviewed by blinded radiologists, and pseudomeningocele size will be measured and recorded.
 - **Visual Analogue Scale**
-

7. Randomization and Blinding

Randomization:

Participants will be randomized in a 1:1 ratio to the interventional or conservative treatment arms using a computer-generated randomization sequence. Randomization will be stratified by age and body mass index.

Blinding:

Due to the nature of the interventions, patients and surgical teams cannot be blinded to group allocation. However, the radiologists interpreting the CT or MRIs and the independent data assessors evaluating outcomes will be blinded to the treatment arm.

8. Sample Size Calculation

A sample size of **60 patients** (30 per group) will be required to detect a clinically significant difference in pseudomeningocele absorption between the two groups, with a power of 80% and an alpha of 0.05.

9. Statistical Analysis

- **Primary outcome:**
The proportion of patients requiring revision surgery for CSF leakage or tension pseudomeningocele at 4 months and 1 year will be compared between the two groups using a chi-square test. Time-to-absorption analyses will be conducted using Kaplan-Meier survival curves and log-rank tests.
 - **Secondary outcomes:**
Infection rates will be compared using Fisher's exact test, and GOSE scores will be analyzed using a Mann-Whitney U test to assess differences in functional recovery between groups.
 - **Multivariate analysis:**
Multivariate logistic regression will be used to adjust for potential confounders, such as baseline health status, age, and type of initial surgery.
-

10. Ethical Considerations

The study will be conducted following the principles of the Declaration of Helsinki. Informed consent will be obtained from all participants before enrollment. The study protocol has been approved by the institutional review board (IRB). The risks associated with interventional approaches (e.g., infection, procedural complications) will be disclosed to patients during the consent process.

11. Follow-up and Monitoring

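### Allocation is balanced on age and BMI, but the severity grade recorded at entry (PPS) is left to chance in a 60-patient trial; adding it by minimisation would be a cheap, modest gain.

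*Protocol*

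**What the plan says.** Section 7 (Randomization) sets 1:1 allocation from a computer-generated sequence and adds: "Randomization will be stratified by age and body mass index". It names no other factor.

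Section 4 (Inclusion Criteria) makes the severity grade a condition of entry: "Diagnosed fluctuation during clinical examination after the surgery, Pseudomeningocele Palpation Scale (PPS), II-IV". The top grade is defined as "IV Tense lesion; painful and/or erythematous; underlying structures are not palpable even with firm pressure".

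Section 6 gives the primary outcome as "New onset of wound CSF leakage or tension pseudomeningocele necessitating revision surgery".

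Section 9 compares the primary proportion between arms with a chi-square test and mentions no covariate for that test. A separate multivariate logistic regression is to adjust for potential confounders, "such as baseline health status, age, and type of initial surgery". That list is open-ended. It names neither PPS nor BMI.

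**The concern.** A stratification factor earns its place by being known before allocation and by being likely to predict the outcome. PPS meets the first condition, because eligibility cannot be settled without it. For the second, the protocol's own wording points the same way: grade IV is a tense lesion, and a tense collection that needs revision surgery is one way to reach the primary event.

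The allocation rule nevertheless does not use PPS, and the primary test does not adjust for it. With 30 patients per arm, chance alone can put noticeably more grade IV patients in one arm, and the crude comparison then carries part of that difference. At stake are some precision and how easily the single result can be read. An analysis plan can add a covariate later, but it cannot change how patients were allocated.

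**Working it through.** **Inputs from the protocol.** 60 patients, 30 per arm, 1:1 (Sections 7 and 8); PPS II-IV at entry (Section 4); crude comparison of proportions (Section 9). Section 8 attaches 80% power and alpha 0.05 to the 60 patients but gives no rates or difference, so that figure can be neither reproduced nor refuted. Only the arm size is used here.

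**Assumptions, not in the protocol.** Share of patients at PPS IV: 10%, 20% or 30% (K = 6, 12 or 18). Event risk: 10% in grades II-III, and 30%, 40% or 50% in grade IV (an excess of 20 to 40 points). No treatment effect.

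**Step 1: chance of an imbalance.** If PPS plays no part in allocation, the number X of grade IV patients in one arm is hypergeometric (60 patients, K at grade IV, 30 drawn). The gap between arms is |2X − K|. A gap of 4 is 4/30 = 13.3 points, and a gap of 6 is 6/30 = 20 points.

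| Grade IV patients | Share | P(gap ≥ 4) | P(gap ≥ 6) |
|---|---|---|---|
| 6 | 10% | 0.19 | 0.02 |
| 12 | 20% | 0.33 | 0.10 |
| 18 | 30% | 0.40 | 0.16 |

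For K = 12, these are a split of 8:4 or worse and of 9:3 or worse. When K is odd the gap is odd too, so a gap of at least 4 means at least 5: the probability is 0.15 for K = 9 and 0.23 for K = 15.

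**Step 2: does age and BMI stratification help?** A simulation assumed four age-by-BMI strata unrelated to PPS and permuted blocks of 4. At grade IV shares of 20% to 40%, a difference of at least 10 points in the grade IV share occurred in 33% to 43% of trials, and of at least 20 points in 8% to 14%. The present factors therefore give little protection. With PPS (IV v II-III) as the only factor, differences of 10 points or more practically vanished; crossed with the four strata, they fell to 2% to 6%. This simulated stratified blocks, not minimisation.

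**Step 3: effect on the crude difference.** Shift = gap × excess risk / 30. For a gap of 6: 6 × 0.20/30 = 4 points; 6 × 0.30/30 = 6 points; 6 × 0.40/30 = 8 points.

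**Step 4: precision.** Take a 20% share and risks of 40% v 10%.
- Overall risk: 0.2 × 0.40 + 0.8 × 0.10 = 0.16.
- Standard error ignoring PPS: √(2 × 0.16 × 0.84/30) = 0.095.
- Mean within-grade variance: 0.2 × 0.40 × 0.60 + 0.8 × 0.10 × 0.90 = 0.120.
- Standard error with PPS balanced and accounted for: √(2 × 0.120/30) = 0.089.
- Variance removed: 1 − 0.120/(0.16 × 0.84) = 11%.

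At the same share, grade IV risks of 30% and 50% give overall risks of 0.14 and 0.18 and within-grade variances of 0.114 and 0.122. The standard errors are then 9.0 v 8.7 points and 9.9 v 9.0 points.

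**The case against.** The choice of stratification factors is a judgement, and the protocol's rule contradicts nothing else in it. No statement in the protocol says that PPS predicts leak or revision, or that age and BMI do not. The link between grade IV and the endpoint is read from the definitions. The grade IV share and the risks are assumptions, and at a 10% share a 20-point imbalance has a probability of only 2%. All of this stands, and it limits the weight of the point.

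The size is also modest. In the central case the 6-point shift is 6/9.5 = 0.63 of one standard error, and it needs a split that occurs in about one trial in ten. Section 9 plans a regression with an open covariate list, so an analysis plan not at hand could add PPS. That would recover part of the precision, but would not change the allocation.

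A reader might infer three stronger things that the documents do not support:
- That treatment and severity could not be told apart. Chance imbalance is already part of the sampling error of a randomised comparison, and adjustment can deal with part of it.
- That open-label teams make the problem worse. They see severity whether or not it is a stratification factor.
- That BMI was a wrong choice and must go. Its absence from an illustrative list of confounders does not show this.

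**Conclusion.** The point holds as a suggestion to consider, not as an error that undermines the trial. Section 7 leaves to chance a grade that is known at entry and close in meaning to part of the primary outcome. On the assumed shares of 10%, 20% and 30%, a gap of 13 points or more in the grade IV share has probability about 19% to 40%, and of 20 points or more about 2% to 16%. A 20-point gap would shift the crude difference by 4 to 8 points if the excess risk in grade IV is 20 to 40 points. The test remains valid on average. The loss is some precision, about 0.5 of a percentage point in the standard error in the central case, and a result that is harder to interpret if the split happens to be uneven. If grade IV is rare or PPS is only weakly prognostic, the gain from the change is smaller still.

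**What to change.** Before the first patient, amend Section 7 so that allocation uses minimisation with a random element on PPS grade (II-III v IV), age and BMI, and so that PPS is recorded before the allocation is released. In Section 9, account for PPS in the primary comparison, for example with a Mantel-Haenszel test stratified by PPS. Without that step the crude chi-square keeps the larger standard error, and the precision gain is not realised. Keeping BMI is compatible with this, since minimisation avoids the sparse cells that crossing three factors would create in 60 patients.

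Cost: a minimisation system has to be set up, with categories for age and BMI, and a few protocol sentences changed. No new data are needed. Downside: PPS is a palpation grade that depends on the examiner's pressure, so misgrading would weaken the benefit. The registration number is still unassigned, which suggests but does not prove that enrolment has not begun. For patients already randomised, only the analysis part of the change could help.

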Title

Conservative versus Interventional Management of Postsurgical CSF
Pseudomeningocele: A Randomized Controlled Trial

NCT number

Not yet assigned

Unique protocol ID

108/20-55/2025

Date

22th May 2026

1. Background and Rationale

Background:

Postsurgical pseudomeningocele formation is a relatively common complication after intracranial surgery, often associated with fluid collection at the surgical site. Management approaches vary, with options including conservative treatment or interventional strategies such as revision surgery, insertion of lumbar drainage, or simple wound puncture. Current evidence on the most effective treatment is limited, and there is a need for randomized controlled trials to evaluate the outcomes of these approaches.

Rationale:

This trial aims to determine whether an interventional approach offers superior outcomes compared to conservative management in terms of pseudomeningocele absorption and overall patient recovery.

2. Objectives and Hypotheses

Primary Objective:

1. New onset of wound CSF leakage necessitating revision surgery

Secondary Objectives:

1. To compare the infection rate between the two treatment groups.
2. To assess functional recovery using the Glasgow Outcome Scale–Extended (GOSE) at 1 year post-surgery.
3. Absorption of pseudomeningocele at 4 months and 1 year post-surgery assessed by CT or MRI
4. Persistence of headache after the surgery – Pain Scale 0-10 (VAS)

Null Hypothesis:

There is no significant difference in the rate of CSF leakage and pseudomeningocele absorption at 4 months and 1 year, as measured by CT or MRI, between patients treated with conservative management and those undergoing interventional procedures (revision surgery, lumbar drainage, or simple puncture). Additionally, there is no significant difference in secondary outcomes, such as infection rates and functional recovery (measured by the Glasgow Outcome Scale–Extended), between the two groups.

3. Study Design

This study is a **parallel-group, randomized controlled trial** with two arms:

- **Interventional Group:** Patients undergoing local treatment - lumbar drainage insertion, simple wound puncture, fibrin glue or any combination.
- **Conservative Group:** Patients managed without surgical procedures, except for skin sutures.

Patients will be followed for a total of 1 year with CT or MRI assessments at 4 months and 1 year post-surgery.

4. Participants / Population

Inclusion Criteria:

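### The primary event counts a leak or tension pseudomeningocele only if it necessitates revision surgery, with no criteria for necessity and no masked judgement of it, so a re-operation threshold that differs by arm can bias the comparison in either direction.

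*Protocol*

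**What the plan says.** **Event.** The primary objective in Protocol Section 2 is "New onset of wound CSF leakage necessitating revision surgery". The primary outcome in Section 6 adds tension pseudomeningocele and keeps the same condition: "New onset of wound CSF leakage or tension pseudomeningocele necessitating revision surgery". Section 9 analyses it in that form: "The proportion of patients requiring revision surgery for CSF leakage or tension pseudomeningocele at 4 months and 1 year will be compared", by chi-square test.

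**Blinding.** Section 7 says that "patients and surgical teams cannot be blinded to group allocation". It adds that radiologists are blinded and that "the independent data assessors evaluating outcomes will be blinded to the treatment arm".

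**Measures short of revision.** In the conservative arm Section 5 allows "no surgical procedures other than the application of skin sutures if required". In the interventional arm Section 3 lists lumbar drain, puncture, fibrin glue or combinations of these. Section 5 lists revision surgery, lumbar drain and puncture for that arm, chosen by clinical judgement.

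**Hypothesis and other outcomes.** The null hypothesis in Section 2 is about the rate of CSF leakage, with no revision condition. The secondary outcomes are infection, GOSE, absorption on imaging and headache on a VAS. None of them counts leaks.

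**The concern.** Whether a leak necessitates revision is a judgement about treatment. If people who know the allocation make it, the recorded rate in each arm is the product of two quantities: how often a leak or tension pseudomeningocele occurs, and how readily such an event is taken to revision. Randomisation balances the arms for the wound's behaviour apart from treatment. It does not balance the second quantity, which may depend on knowing the arm and on which lesser measures are available there.

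A blinded assessor who records that a revision took place does not correct this, because the selection has already happened. Leaks managed in other ways are not an outcome, so the comparison in the null hypothesis could not be recovered from the planned outcomes. A larger sample would estimate the biased difference more precisely and would not remove it.

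**Working it through.** **Step 1: the passages side by side.**

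| Question | What the protocol gives |
|---|---|
| Condition for counting the event | Revision surgery necessitated or required (Sections 2, 6, 9) |
| Criteria for necessity | None |
| Who judges necessity | Not stated |
| Masked adjudication of necessity | None described; Section 7 names blinded assessors of outcomes in general |
| Measures short of revision, conservative arm | Skin sutures (Sections 3, 5) |
| Measures short of revision, interventional arm | Drain, puncture, glue (Section 3); drain, puncture (Section 5) |
| Revision surgery as assigned treatment | Listed in Section 5 and in the null hypothesis; absent from the arm description in Section 3 |
| Outcome counting leaks however managed | None |

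On the Section 5 reading, the same operation can be both the assigned treatment and the primary event.

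**Step 2: the plan's own figure.** Section 8 gives 60 patients, 30 per group, for a difference in absorption at 80% power and alpha 0.05. It gives no absorption rates, so the figure can be neither confirmed nor refuted. Only the 30 per group is used below.

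**Step 3: how large the bias could be.** Let L be the true rate of leak or tension pseudomeningocele, the same in both arms, and let r be the probability that such an event goes to revision. The recorded rate in an arm is p = L × r. L and r are assumptions, because the protocol gives neither.

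The recorded difference is L × (r₁ − r₂), which does not depend on sample size. With r = 0.9 and 0.5 it is 0.20 × 0.4 = 8 points at L = 20%, and 0.50 × 0.4 = 20 points at L = 50%.

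The false rejection rate is the sum, over all event counts i and j from 0 to 30, of Bin(i; 30, p₁) × Bin(j; 30, p₂) wherever |z| > 1.96. Here z = [(i − j)/30] / √[p̄(1 − p̄) × 2/30] and p̄ = (i + j)/60. This is the two-sided chi-square test without continuity correction. Cells show the recorded rates and then the rejection rate.

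| True rate L, both arms | r 0.8 vs 0.8 | r 0.9 vs 0.5 | r 0.8 vs 0.4 | r 0.9 vs 0.3 |
|---|---|---|---|---|
| 20% | 16% vs 16%: 5.2% | 18% vs 10%: 14.8% | 16% vs 8%: 16.5% | 18% vs 6%: 31.6% |
| 30% | 24% vs 24%: 4.9% | 27% vs 15%: 20.2% | 24% vs 12%: 22.4% | 27% vs 9%: 45.2% |
| 40% | 32% vs 32%: 4.8% | 36% vs 20%: 27.9% | 32% vs 16%: 30.3% | 36% vs 12%: 60.0% |
| 50% | 40% vs 40%: 4.9% | 45% vs 25%: 36.3% | 40% vs 20%: 39.2% | 45% vs 15%: 73.7% |

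Equal thresholds keep the test near 5%, and so does counting every event however managed (r = 1 in both arms). The table is symmetric: swapping the arms gives the same rejection rate with the sign of the difference reversed.

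**The case against.** **A severity threshold is defensible.** A leak serious enough to need re-operation matters to patients, and the condition is stated in Sections 2, 6 and 9 alike. This stands as a reason to keep revision surgery as a reported outcome. It does not supply criteria for necessity or masking of that judgement.

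**The protocol does not say that the unblinded surgeon decides.** A reader might infer that the event exists only by an unblinded surgeon's decision and that blinded assessors can do no more than confirm an operation. That is the natural reading, but it is not in the text. Section 7 has blinded assessors evaluating outcomes, and masked judgement of need could be set out in a document not shown. What stands against the protocol is that it fixes the endpoint on necessity and leaves that term without criteria.

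**The route to revision is not described.** A reader might infer that conservative-arm patients with a leak cross over to a drain or puncture, or that interventional-arm leaks reach revision once other options are used up. The protocol contains neither sequence. Nor does it say that sutures are used to close leaks, although that is a plausible use.

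**Direction.** Missed conservative-arm events are one possibility. The opposite is equally open, since the interventional arm has more alternatives to revision.

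**One-patient p-values prove little here.** By uncorrected chi-square, 4 vs 0 events of 30 gives p = 0.038 and 3 vs 0 gives 0.076, so one reclassified patient appears decisive. That fragility belongs to any binary endpoint at this size and is not evidence of biased ascertainment. It also depends on the test: Fisher's exact test gives 0.112 and 0.237.

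**Adverse events are recorded.** Section 11 has them recorded and reported to the IRB, so some leaks managed without revision may be on file. They are still not a defined or compared outcome.

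**Conclusion.** The concern holds as a weakness in how the primary endpoint is fixed. The event depends on a judgement of necessity that has no stated criteria and no described masking, in a trial with unblinded surgical teams and different lesser measures by arm. Leaks managed without revision enter no outcome, so the endpoint does not match the null hypothesis on the leak rate.

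The size is illustrative. With no true difference, assumed re-operation probabilities of 0.9 against 0.5 take false rejection from about 5% to about 15% to 36% for true rates of 20% to 50%. A smaller gap does less harm, a wider one more. The documents give no event rates or re-operation probabilities and do not settle the direction.

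A reader might conclude that the trial's blinding fails altogether. The documents do not support that: masked reading of the scans does protect the absorption outcome. The point concerns the revision-based primary event only.

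**What to change.** 1. In Sections 6 and 9, define the event as a new post-randomisation wound CSF leak or new tension pseudomeningocele that meets criteria fixed in advance, however it is then managed. Align Section 2 with this.
2. State how patients already at PPS IV at baseline can have the tension event. Section 4 admits PPS II to IV, so a rule based on progression to grade IV cannot apply to them.
3. Have the blinded assessors named in Section 7 adjudicate each suspected event from records with the allocation masked.
4. Report revision surgery, and any procedure outside the assigned arm, separately by arm.
5. Reconcile Section 3 with Section 5 on whether revision surgery is an interventional-arm treatment, and state that a procedure given as assigned treatment is not itself a primary event.

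The cost is protocol wording and masked case summaries for assessors already planned. The endpoint will include some milder leaks that would not have led to re-operation; reporting revision separately keeps that information. Leaks and palpation grade are still noticed and recorded at the bedside by people who know the arm, so the bias is reduced and not removed.

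### Section 8 justifies 60 patients and 80% power only for absorption, while the protocol contradicts itself on the primary endpoint and shows no power for the declared one

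*Protocol*

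**What the plan says.** All references are to the protocol.

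- **Section 8 (Sample Size Calculation).** The total is 60, split equally into two arms of 30, and is described as "required to detect a clinically significant difference in pseudomeningocele absorption between the two groups, with a power of 80" per cent. Alpha is set at 0.05. Absorption is the only endpoint named. No rates, difference, standard deviation or time point are given, and the sidedness of alpha is not stated.
- **Section 2 (Objectives).** The primary objective is "New onset of wound CSF leakage necessitating revision surgery". Absorption on imaging at 4 months and 1 year is the third secondary objective.
- **Section 6 (Outcomes).** The primary outcome is "New onset of wound CSF leakage or tension pseudomeningocele necessitating revision surgery". Absorption is listed under the secondary outcomes, but the text of that entry calls resolution or reduction of the collection the primary outcome.
- **Section 9 (Statistical Analysis).** Under the primary-outcome heading: "The proportion of patients requiring revision surgery for CSF leakage or tension pseudomeningocele at 4 months and 1 year will be compared", by chi-square test. The next sentence under the same heading plans Kaplan-Meier curves and log-rank tests for time to absorption.
- **Section 7 (Randomization).** "Participants will be randomized in a 1:1 ratio to the interventional or conservative treatment arms".

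**The concern.** A power statement belongs to one endpoint, one test and one assumed difference. The only such statement here is attached to absorption, while the headings of Sections 2 and 6 and the chi-square test in Section 9 make revision surgery the primary comparison. A reader who sees 80% power in Section 8 will naturally carry it over to the primary test, and nothing in the protocol supports that.

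Two things are at stake. First, the trial's main question is not fixed: two endpoints are each called primary somewhere, so whichever gives the clearer result could later be presented as the planned one. Second, if revision surgery is the primary endpoint, the protocol does not say how large a difference 30 per group could detect, so a non-significant result would be hard to interpret.

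**Working it through.** **1. Inputs.** From the protocol: 30 per group, 1:1 allocation, power 80%, alpha 0.05, chi-square test of proportions for revision surgery. Not in the protocol: event rates for revision surgery, absorption rates, sidedness. I assume two-sided 0.05 and a range of rates. Every rate below is an assumption.

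**2. Can the plan's 60 be reproduced?** No, because the difference is described only as clinically significant. It can only be back-solved, that is, by asking what 30 per group would detect on absorption. Exact power of the uncorrected chi-square test:

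| Assumed absorption rates | Difference | Power |
|---|---|---|
| 40% vs 75% | 35 points | 80.2% |
| 50% vs 83.5% | 33.5 points | 80.5% |
| 60% vs 90% | 30 points | 79.6% |
| 80% vs 99.2% | 19.2 points | 80.4% |

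If absorption were instead analysed as a mean size, the detectable standardised difference would be (1.960 + 0.842) × √(2/30) = 2.802 × 0.258 = 0.72. So 60 is a possible answer for absorption under several sets of assumptions, but it cannot be verified.

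**3. Power for revision surgery at the same size.** For each pair of rates p1 and p2, take the sum over all tables (a, b) of Bin(a; 30, p1) × Bin(b; 30, p2), counting only tables where the test gives p ≤ 0.05. The protocol does not say whether the chi-square is continuity-corrected, so both forms are shown.

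| Assumed rates | Uncorrected chi-square | Continuity-corrected |
|---|---|---|
| 10% vs 5% | 11% | 2% |
| 20% vs 10% | 19% | 10% |
| 20% vs 5% | 45% | 24% |
| 30% vs 10% | 50% | 37% |
| 30% vs 5% | 78% | 63% |
| 20% vs 0.1% | 87% | 56% |

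**4. Difference needed for 80%** (uncorrected, exact):

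| Lower rate | Higher rate needed | Difference |
|---|---|---|
| 0% | 17.7% | about 18 points |
| 1% | 20.5% | 19.5 points |
| 2% | 23.3% | about 21 points |
| 5% | 31% | 26 points |
| 10% | 40.2% | about 30 points |
| 20% | 54.3% | about 34 points |
| 40% | 75% | 35 points |

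**5. Scale, for one assumed case (20% vs 10%).** The number per arm for 80% power is [1.960 × √(2 × 0.15 × 0.85) + 0.842 × √(0.20 × 0.80 + 0.10 × 0.90)]² / 0.10² = (0.990 + 0.421)² / 0.01 ≈ 199. With 30 per arm, the half-width of the 95% confidence interval for the risk difference is 1.960 × √(0.16/30 + 0.09/30) = 1.960 × 0.0913 = 0.179, or about 18 points either side.

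**The case against.** The strongest reply is that absorption may be the intended primary endpoint. The rationale in Section 1 speaks of superiority in absorption. The null hypothesis in Section 2 places absorption beside CSF leakage and apart from the secondary outcomes. The Section 6 absorption entry calls itself primary, and Section 9 puts time-to-absorption under the primary heading. On that reading Section 8 is sized on the right endpoint. This stands as a reason to settle the endpoint first. It does not rescue the text, because the headings of Sections 2 and 6 and the chi-square test in Section 9 then have to change.

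Four stronger readings are tempting, and the documents do not support them:

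- *The primary outcome lacks 80% power.* No event rates are given, so this is conditional. With a rate near zero in one arm, about 18 to 20 points suffices (step 4). What can be said is that 80% power is not shown.
- *Even absorption needs 33 to 35 points.* That holds for lower rates of roughly 20% to 50%. At 80% vs 99.2% the difference is about 19 points. Absorption also need not be analysed as a simple proportion, since size is to be measured and a log-rank test is planned.
- *The 60 makes no allowance for loss to follow-up.* Section 8 is silent, so whether a margin is included is unknown.
- *The primary result will most likely be non-significant, and would be read as equivalence.* The first part depends on unknown rates. The second is not proposed anywhere in the protocol, which aims at superiority.

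A statistical analysis plan may hold the missing rates. That would explain the 60, but it would not remove the contradiction between sections of the protocol itself.

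**Conclusion.** The point holds in this form: the protocol names two different endpoints as primary in different places, and its only sample-size justification is for the one that Sections 2 and 6 list as secondary. That much rests on the text alone and needs no assumption.

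The size of the consequence is conditional. If revision surgery is primary, 30 per group gives about 11% to 50% power for the assumed differences of 5 to 20 points in which the lower rate is 5% or 10%. It reaches 80% only for differences of about 18 to 35 points over lower rates of 0% to 40%. These figures assume a two-sided 0.05 level, the uncorrected chi-square test and all 30 per group evaluable. A continuity correction lowers them.

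**What to change.** Keep 60 patients and change the wording, in this order.

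1. Name one primary endpoint and make Sections 2, 6, 8 and 9 agree. This includes the sentence in the Section 6 absorption entry, the place of time-to-absorption in Section 9, and whether tension pseudomeningocele belongs to the primary objective in Section 2 as it does to the outcome in Section 6.
2. If revision surgery stays primary, say in Section 8 that the 80% refers to absorption, with its two assumed proportions and time point. Then state the difference in revision surgery that 30 per group can detect and the expected width of the 95% confidence interval for the risk difference.
3. If absorption is the intended primary, declare it so in Sections 2, 6 and 9, and give in Section 8 the assumed rates and time point behind the 60.

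The cost is protocol wording only, and the protocol shows no registration number assigned yet. The downside is that the stated power for the primary outcome may become less favourable. Under option 2 the trial would openly have no 80% power claim for its primary comparison unless the expected difference is as large as those in step 4.
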